# Study Protocol

## Study Objectives

Our first aim is to integrate three distinct 'nudge' alerts into the UCLA Health EHR. Each nudge will test a different behavioural economics framing strategy. Our second aim is to conduct a four-arm randomised pragmatic trial to compare the effectiveness of the nudges to each other and to usual care. We hypothesise that exposure to the nudges will result in a reduction of pre-op tests ordered by physicians. We will randomise providers who conduct pre-op visits for patients with cataract surgery to one of four study arms: nudge 1, nudge 2, nudge 3 or no nudge (usual care) and measure the effect of the intervention on pre-op testing (see below).

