## Trial design

This is a pragmatic, parallel group, open-label, randomised controlled superiority trial. Groups are allocated 1:1 to the intervention arms (nudges) and control arm (routine care). This trial will be conducted between June 2021 and June 2022 with a 12-month follow-up period. This trial has been registered with the United States Clinical Trials Registry. This protocol manuscript is compliant with the Standard Protocol Items: Recommendations for Interventional Trials statement. In this pragmatic trial of a quality improvement intervention, neither patients nor physicians provide consent to participate in the trial. This protocol was approved by the Institutional Review Board (IRB) of the University of California, Los Angeles (IRB#18-0 01 240).

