### Primary and secondary outcome analysis

We will measure and compare rates of testing in the 12 months before and 12 months after initiation of the randomisation (primary outcome) to determine whether the EHR-based intervention is successful in changing physician behaviour. We will also compare each of the three intervention arms and the usual care arm and will perform exploratory comparisons between nudge 1, nudge 2 and nudge 3 (secondary outcome) to determine whether certain behavioural economic framing techniques are more effective than others at reducing pre-op testing.

Other secondary outcomes will include the percentage of patients who received specific categories of pre-op tests including labs, EKGs and CXRs, same-day surgery cancellations and physician-level

experience measured by the surveys. We will also estimate cost savings associated with the intervention (described below). Evaluation of the primary and secondary outcomes will be performed using generalised linear mixed-effects models at the patient level. We will investigate the impact of all nudges versus control, which will require a threefold correction. As a secondary analysis, we will conduct pairwise comparisons of the nudges. Models will include fixed nudge 1, nudge 2 and Nudge 3 effects, a fixed study period effect (postnudge intervention vs prenudge intervention), second-order interactions between these effects, a fixed stratum effect (hospitalist vs PCP) and random physician effects. Physician effects will account for clustering of patients by physician. Comparisons between changes in utilisation rates across study arms will be estimated and tested using model contrasts. All pairwise comparisons of changes between study arms will be performed to identify the most effective nudge, and Bonferroni corrections will be applied to control the familywise type I error rate at 5%. Intervention effects will be summarised using ORs, 95% CIs and p values (with multiple comparison corrections). Differences between strata will be similarly summarised.

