### Power

Preliminary analyses of UCLA Health data show that the baseline rate of testing is 65%. In a prior quality improvement study conducted at a different health system, we reduced pre-op lab testing by 59% (a reduction from 90% to 31%). We conservatively estimate an effect half as large (30%) in each intervention arm.

To calculate savings from reduced use of medical services, we will multiply the estimates of utilisation (ie, quantity) for each of the pre-op services measured by the relevant payment rates for the services based on the coverage type for the patient (ie, Medicare and average commercial payment rates per service). We will then compare differences in spending overall and by specific services (ie, lab testing, EKGs) between the control arm and each of the intervention arms and a pooled estimate of the three-nudge intervention arms. We will disaggregate the savings to measure the amount and proportion accrued by the health system/payer versus the patient. An extension of this analysis will estimate how reducing the utilisation of pre-op testing affect different parties; we will disaggregate the savings estimates by type of payer contract (ie, capitated vs fee-for-service(FFS)) to derive estimates of savings to the health systems versus the payer. Under capitated payments, the savings accrue to the health system, while under FFS payments, the savings accrue to the payer and represent revenue losses for the health system.

We will extrapolate observed saving estimates to compute savings the Medicare FFS programme might expect to accrue if similar reductions in the utilisation of pre-op services for cataract surgery were observed in the Medicare population. To generate these savings estimates, we will compute the number of Medicare patients undergoing cataract surgery in a single year and the fraction of patients who have these pre-op tests. We will then take our estimates of reduction in utilisation and apply these estimates to the current use of pre-op testing utilisation in the Medicare FFS programme to determine the number

of services that would be reduced. We would then apply FFS payment rates to the number of services that would be reduced to estimate savings to Medicare. Finally, we will develop estimates of longer term savings in a year–year time range, applying a discount rate to costs, assuming that the observed reduced amount of services used remained similar after the 1-year study period ended.

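### Bonferroni for the three nudge-versus-control contrasts is valid but less powerful than Holm when more than one nudge works, and the plan does not say whether its 95% CIs are adjusted

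*Combined protocol and SAP*

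**What the plan says.** Physicians are randomised to "one of four study arms: nudge 1, nudge 2, nudge 3 or no nudge (usual care"), so all three nudges are compared with the same usual-care arm. The Trial design section says "Groups are allocated 1:1 to the intervention arms (nudges) and control arm (routine care"), which I read as four equal arms.

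The SAP section on primary and secondary outcome analysis then says three things about multiplicity:

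- For the control comparisons: "We will investigate the impact of all nudges versus control, which will require a threefold correction".
- For the arm-to-arm comparisons: "All pairwise comparisons of changes between study arms will be performed to identify the most effective nudge", and in the same sentence "Bonferroni corrections will be applied to control the familywise type I error rate at 5" percent. No other multiplicity procedure is named.
- For reporting: "Intervention effects will be summarised using ORs, 95% CIs and p values (with multiple comparison corrections").

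The Power section gives a baseline ("the baseline rate of testing is 65" percent) and a common expected effect: "We conservatively estimate an effect half as large (30%) in each intervention arm". It states no target power, sample size or intraclass correlation (ICC).

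**The concern.** Single-step Bonferroni holds every contrast to p < 0.0167, even after the other nudges have been shown to work. A step-down procedure relaxes the later thresholds and keeps familywise error at 5%. Because the planning assumption is that all three nudges work equally well, the trial is designed around the situation in which the single-step method gives away most. An effective nudge could be reported as unproven because of the procedure alone.

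The second issue is the intervals. The reporting sentence gives a 95% level and puts the correction in a bracket at the end. If the bracket covers only the p values, a contrast with raw p between 0.0167 and 0.05 would have an interval excluding OR 1 beside a non-significant corrected p. The main result could then be read either way.

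**Working it through.** **Inputs from the documents.** Familywise error 5%; three control contrasts; one shared control; 1:1 allocation; baseline 65%; expected effect 30%; 322 physicians and 1122 visits in 2019 (Inclusion Criteria), so 1122/4 = 280.5 visits per arm and 1122/322 = 3.48 per physician.

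**Assumed.** Two-sided tests, four equal arms, normal test statistics, equal effects unless stated, 2019 volumes repeated in each period, independent before and after samples, ICC between 0 and 0.5.

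**1. The plan's own figure.** 0.05/3 = 0.0167 per test, |z| > 2.394, and 3 × 0.0167 = 5.0%. The stated bound is reproduced.

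**2. Actual familywise error.** Two contrasts sharing a control have covariance σ²/n and variance 2σ²/n, so their correlation is 0.5. Then

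FWER(c) = 1 − ∫ φ(u) [Φ(√2·c − u) − Φ(−√2·c − u)]³ du.

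- c = 2.394 (Bonferroni): 4.45%.
- c = 2.349 (single-step Dunnett): 5.0%.
- c = 1.960 (no adjustment): 12.5%, so joint coverage of three unadjusted 95% CIs is 87.5%.

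**3. Power of the step-down tests.** Holm takes the contrasts in order of p and compares them with 0.05/3, 0.05/2 and 0.05, stopping at the first failure. Simulated with correlation 0.5 and all three nudges equally effective:

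| Bonferroni, per contrast | Holm, per contrast | Bonferroni, all three | Holm, all three |
|---|---|---|---|
| 60% | 68% | 35% | 52% |
| 70% | 78% | 47% | 64% |
| 80% | 86% | 61% | 77% |
| 90% | 94% | 78% | 89% |

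Step-down Dunnett is within about 1 point of Holm throughout. Single-step Dunnett gains little (80.0% to 81.2%), so the benefit comes from stepping down.

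At 80% Bonferroni power per effective nudge:

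- Two nudges work: power to show both goes from 69% to 74% with Holm.
- One nudge works: power goes from 80.0% to 80.1% with Holm.
- All three work: the chance of showing at least one is 95.0% under both.

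**4. Where this trial might sit.** For a before-after change compared between arms,

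power = Φ( d / √[(3·p₁(1−p₁) + p₂(1−p₂))/n_eff] − 2.394 ), with n_eff = 280.5 / (1 + 2.48·ICC).

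- 30% as points (65% to 35%): ICC 0 gives 0.30/√(0.91/280.5) = 5.27, power 99.8%. ICC 0.5 gives n_eff = 125, 0.30/√(0.91/125) = 3.52, power 86.9%.
- 30% as a relative reduction (65% to 45.5%): ICC 0 gives 0.195/√(0.930/280.5) = 3.39, power 83.9%. ICC 0.5 gives 2.26, power 44.7%.

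A comparison of the post period alone, on the points reading, has power of 99.3% or more.

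**5. Interval and test disagreement, if the CIs are unadjusted.** Per contrast the probability is Φ(δ − 1.960) − Φ(δ − 2.394).

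- 80% power: δ = 2.394 + 0.842 = 3.236, giving 0.899 − 0.800 = 9.9%.
- 60% power: δ = 2.394 + 0.253 = 2.647, giving 0.754 − 0.600 = 15.4%.

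**The case against.** The strongest reply is that nothing here is broken. Bonferroni controls the stated error rate, it is pre-specified, and 98.33% intervals would match it exactly. This stands: a reader might infer that the multiplicity plan is wrong, but the documents show only a valid, somewhat conservative choice.

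A reader might also infer that the plan prescribes ordinary 95% CIs, so that intervals and tests will conflict. The text does not say so. The closing bracket can be read as covering the intervals as well as the p values. The 87.5% coverage and the 10-15% disagreement are therefore conditional on one reading. What can be said is that the plan does not settle the question.

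Third, the gain may be small in this trial. The source effect is 90% − 31% = 59 points, and half is 29.5, so the points reading of 30% is the more natural one. Power may then already be high. This stands in part: near 99% the gain is under 1 point per contrast. But with an unknown ICC, the before-after contrast falls to 87% on the points reading and to 45-84% on the relative reading.

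Fourth, step-down tests lack simple matching intervals. With step-down Dunnett tests and single-step Dunnett CIs, the interval includes 1 for a rejected contrast in about 6-7% of contrasts, and this happens at least once in 16-19% of trials, at 60-80% Bonferroni power. This stands, so the SAP must say which result decides.

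Finally, the Bonferroni sentence refers to all pairwise comparisons, of which four arms give six. The threefold sentence supports a factor of 3 for the control contrasts, but the two should be separated explicitly. A factor of 6 would cut power from 80.0% to 72.5%.

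**Conclusion.** The point holds as an efficiency improvement and a request for clarity. It is not an error, and no planned conclusion becomes invalid. Holm rejects everything that threefold Bonferroni rejects, sometimes more, and needs no assumption about correlation to keep familywise error at 5%. If all three nudges work equally well and Bonferroni power is 60-80% per contrast, the gain is about 6-8 points per contrast and 16-17 points for showing all three. Those power levels are assumed. The gain shrinks as power approaches 99%, is almost nil if only one nudge works, and does not raise the chance of showing at least one nudge effective. The size of the gain rests on equal arms, correlation 0.5 and two-sided tests. The status of the CIs is unresolved in the text and should be settled before analysis.

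**What to change.** In the SAP section on primary and secondary outcome analysis:

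1. For the three nudge-versus-control contrasts, replace Bonferroni with Holm, or with step-down Dunnett on the planned model contrasts, at 5% familywise error. State that these three form their own family, separate from the between-nudge comparisons.
2. State that the step-down test decides whether a nudge is declared effective.
3. Report simultaneous CIs for the three contrasts, labelled descriptive: 98.33% intervals alongside Holm, or Dunnett intervals (critical value about 2.35) alongside step-down Dunnett. Say explicitly that the intervals are adjusted.

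The cost is a few sentences and a step applied to contrasts already planned; no new data are needed. The downside is that an interval can include 1 for a contrast rejected at a later step. With Dunnett intervals this affects about 6-7% of contrasts at 60-80% Bonferroni power. With Holm and 98.33% intervals it equals the power gain (68 − 60, 78 − 70, 86 − 80), so about 6-8%. The 98.33% intervals are 2.394/1.960 = 1.22 times as wide as 95% intervals on the log-OR scale. If exact agreement between test and interval matters more than power, keeping Bonferroni with 98.33% CIs is a coherent alternative, provided the SAP says so.

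### Same-day surgery cancellation is analysed nudge by nudge with corrected p values and no pooled nudges-versus-control contrast, so at low baseline rates a tripling would probably be non-significant

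*Combined protocol and SAP*

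**What the plan says.** All of the analysis wording is in the SAP section Primary and secondary outcome analysis.

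- Cancellation is listed among the other secondary outcomes: "labs, EKGs and CXRs, same-day surgery cancellations and physician-level" experience.
- One model family serves everything: "Evaluation of the primary and secondary outcomes will be performed using generalised linear mixed-effects models at the patient level".
- The nudges enter separately and interact with period: "Models will include fixed nudge 1, nudge 2 and Nudge 3 effects, a fixed study period effect". The effect of a nudge is therefore its before/after change minus the change in control.
- On multiplicity: "We will investigate the impact of all nudges versus control, which will require a threefold correction". For the pairwise comparisons of changes between arms, "Bonferroni corrections will be applied to control the familywise type I error rate at 5" per cent.
- On reporting: "Intervention effects will be summarised using ORs, 95% CIs and p values (with multiple comparison corrections"). No outcome is exempted.

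The Power section, which also holds the cost analysis, compares spending between control and each intervention arm and adds "a pooled estimate of the three-nudge intervention arms". No such pooled estimate is mentioned for cancellation. The same part of the SAP admits inadequate power for serious complications and makes the 30-day cardiovascular comparison exploratory; it gives no comparable caution for cancellation.

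**The concern.** Familywise correction guards against claiming a benefit that is not there. For an outcome where the worry is a rise, the costly error is missing one, and a correction makes that error more likely.

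Splitting the intervention three ways also costs precision. Under Three Intervention Arms, the alerts share the hard stop, the one-click removal of the order and the assurance that the pre-op centre will order what is needed on the day. They differ in the framing phrase and image. If fewer tests led to more cancellations, any nudge versus none would be the natural first question, and the plan already accepts that pooling for spending.

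At stake is how a null result is read. Three non-significant corrected p values could be taken as reassurance that surgery was not disrupted, when the contrast could not have shown even a large increase.

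**Working it through.** **The plan's own figure.** There is none to reproduce: the documents give no baseline rate, detectable difference or power for cancellation.

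**Inputs.**
- 1122 pre-op visits in 2019 (Inclusion Criteria). Four arms, taken as equal (Trial design), give n = 1122/4 = 280.5 visits per arm per 12-month period.
- Two-sided tests (assumed; sidedness is not stated). Threefold correction: 0.05/3, z = 2.394. Uncorrected: z = 1.960.
- Cancellation rate p: assumed at 1%, 2%, 3% and 5%. Expected events per arm-year are 280.5 × p = 2.8, 5.6, 8.4 and 14.0.
- Clustering and covariates ignored, which favours the plan.

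**Threshold for significance.** With v = 1/(np) + 1/(n(1−p)), the standard error of the before/after log odds ratio contrast is √(4v) for one nudge versus control. For three pooled nudges versus control it is √(2v + 2v/3) = √(8v/3). The threshold is exp(z × SE).

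At p = 2%: v = 1/5.61 + 1/274.89 = 0.1819.
- Single nudge, corrected: SE = 0.853; exp(2.394 × 0.853) = 7.7.
- Pooled, uncorrected: SE = 0.696; exp(1.960 × 0.696) = 3.9.

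This holds all cells at the baseline event count. If the post-period nudge cell is allowed to hold the extra events that the observed ratio implies, the thresholds fall. The table gives both values (lower = cell allowed to vary).

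| Assumed rate | Single nudge, corrected | Pooled, uncorrected |
|---|---|---|
| 1% | 12.5–17.7 | 6.2–6.8 |
| 2% | 6.2–7.7 | 3.7–3.9 |
| 5% | 3.3–3.7 | 2.3–2.4 |

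**Power if the rate triples,** same before/after contrast. The third column is the simulated chance that at least one of the three corrected contrasts is significant when all three nudges triple the rate.

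| Control rate → nudge rate | One nudge, 0.05/3 | Any of three, 0.05/3 | One nudge, 0.05 | Pooled, 0.05 |
|---|---|---|---|---|
| 1% → 3% | 8.5% | 6% | 17% | 22% |
| 2% → 6% | 17.5% | 26% | 31% | 40% |
| 3% → 9% | 28% | 44% | 44% | 56% |
| 5% → 15% | 50% | 71% | 67% | 80% |

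The single-nudge and pooled columns are normal approximations. At 1% the approximation is optimistic for one nudge (simulation gives about 2%), which is why the simulated third column can lie below it. A design effect of 1.25 for clustering lowers the 2% row to about 14% (one nudge, corrected) and 33% (pooled).

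**What drives the threshold at 2%** (fixed-cell formula, starting from 7.7):
- drop the correction only: exp(1.960 × 0.853) = 5.3;
- pool only, still corrected: exp(2.394 × 0.696) = 5.3;
- keep one nudge and the correction, but compare the post period only: exp(2.394 × √(2v)) = 4.2;
- pool and drop the correction, keeping the before/after contrast: 3.9.

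**Risk-difference scale at 2%.** The half-width of an ordinary 95% CI for the before/after contrast is 1.960 × √(4 × 0.02 × 0.98/280.5) = 3.3 percentage points for one nudge. Pooled, it is 1.960 × √((8/3) × 0.02 × 0.98/280.5) = 2.7 points.

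**The case against.** Several points on the other side stand.

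- **Savings are not analysed only in pooled form.** A reader might infer a plan that pools for benefit and splits for harm. The Power section compares spending arm by arm as well. The gap is only that cancellation lacks the pooled estimate.
- **The documents do not name cancellation as the harm outcome.** It is one of several secondary outcomes, with no safety hypothesis, and nowhere does the plan say it will read non-significance as no disruption.
- **The reach of the correction is a reading of general wording.** Bonferroni is described in connection with changes in utilisation and finding the most effective nudge. Still, the model sentence covers all secondary outcomes and the reporting sentence exempts none.
- **Ordinary 95% CIs may already be intended.** The parenthesis about corrections most naturally attaches to the p values. A large odds ratio would then be visible beside a non-significant p value. A corrected interval (half-width 4.0 points at 2%, from z = 2.394) should not be assumed, so the fair gain from pooling is 3.3 to 2.7 points.
- **The correction and the splitting are not the main cause.** Few events and the before/after contrast matter as much, as the post-period threshold of 4.2 shows.
- **Pooling assumes similar effects.** Framings that reduce testing by different amounts could affect cancellation differently. That is a reason to keep per-nudge results on display.

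A reader might also infer that the 30-day cardiovascular events are caught by the correction. The SAP makes them exploratory and does not say they are corrected, so they need no removal from a corrected set.

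**Conclusion.** The point holds in a limited form. The plan specifies no pooled, uncorrected look at cancellation, and adding one would bring a clear gain in precision: at an assumed 2% rate the threshold falls from about 6.2–7.7 to 3.7–3.9.

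It is not supported to say that a several-fold rise would certainly be missed. That depends on a rate the documents do not give. Up to about 3%, a tripling would more likely than not be non-significant (6% to 44% chance that any corrected contrast flags it). At 5% the chance of at least one flag is 71%.

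Nor does pooling cure the problem. Power for a tripling is still only 22% to 40% at rates of 1% to 2% and reaches 80% only at about 5%. How the result is worded therefore matters as much as the contrast.

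These figures assume 1122 visits a year, equal arms, two-sided tests and no clustering. If the correction family is all six pairwise contrasts (0.05/6), the single-nudge figures get worse.

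**What to change.** In Primary and secondary outcome analysis:

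1. Make the lead analysis of "same-day surgery cancellations" the three nudges pooled versus control.
2. Report it as an absolute risk difference with an uncorrected 95% CI, and interpret the upper limit rather than a p value.
3. Keep the per-nudge cancellation results as descriptive.
4. State that a non-significant result is not evidence of no increase, and give the expected cancellation rate from the health system's own records so that readers can judge what could be seen.
5. Say whether the 95% CIs elsewhere are corrected or ordinary.

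The cost is SAP wording and one extra model contrast; no new outcome data are needed. The downside is a slightly higher chance of a false signal of harm, which is the more acceptable error for this outcome. The wording on cardiovascular events can stay as it is.

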### Power

Preliminary analyses of UCLA Health data show that the baseline rate of testing is 65%. In a prior quality improvement study conducted at a different health system, we reduced pre-op lab testing by 59% (a reduction from 90% to 31%). We conservatively estimate an effect half as large (30%) in each intervention arm.

To calculate savings from reduced use of medical services, we will multiply the estimates of utilisation (ie, quantity) for each of the pre-op services measured by the relevant payment rates for the services based on the coverage type for the patient (ie, Medicare and average commercial payment rates per service). We will then compare differences in spending overall and by specific services (ie, lab testing, EKGs) between the control arm and each of the intervention arms and a pooled estimate of the three-nudge intervention arms. We will disaggregate the savings to measure the amount and proportion accrued by the health system/payer versus the patient. An extension of this analysis will estimate how reducing the utilisation of pre-op testing affect different parties; we will disaggregate the savings estimates by type of payer contract (ie, capitated vs fee-for-service(FFS)) to derive estimates of savings to the health systems versus the payer. Under capitated payments, the savings accrue to the health system, while under FFS payments, the savings accrue to the payer and represent revenue losses for the health system.

We will extrapolate observed saving estimates to compute savings the Medicare FFS programme might expect to accrue if similar reductions in the utilisation of pre-op services for cataract surgery were observed in the Medicare population. To generate these savings estimates, we will compute the number of Medicare patients undergoing cataract surgery in a single year and the fraction of patients who have these pre-op tests. We will then take our estimates of reduction in utilisation and apply these estimates to the current use of pre-op testing utilisation in the Medicare FFS programme to determine the number

of services that would be reduced. We would then apply FFS payment rates to the number of services that would be reduced to estimate savings to Medicare. Finally, we will develop estimates of longer term savings in a year–year time range, applying a discount rate to costs, assuming that the observed reduced amount of services used remained similar after the 1-year study period ended.

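### Does the unlabelled 59% and 30% in the Power section leave the planning effect, and so the power, in doubt?

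*Combined protocol and SAP*

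**What the plan says.** The Power section of the Statistical Analysis Plan gives three figures. Preliminary health-system data show that "the baseline rate of testing is 65" per cent. In a quality improvement study elsewhere, "we reduced pre-op lab testing by 59% (a reduction from 90% to 31" per cent). From this the plan moves to its own assumption: "We conservatively estimate an effect half as large (30%) in each intervention arm". It prints no expected post-intervention rate, power, target sample size or intraclass correlation (ICC).

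Under Primary and secondary outcome analysis, the test concerns differences between arms in pre-to-post change: "Comparisons between changes in utilisation rates across study arms will be estimated and tested using model contrasts". On multiplicity, "We will investigate the impact of all nudges versus control, which will require a threefold correction", and for the full set of pairwise comparisons "Bonferroni corrections will be applied to control the familywise type I error rate at 5" per cent. Results are reported on the odds ratio scale: "Intervention effects will be summarised using ORs, 95% CIs and p values (with multiple comparison corrections".

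For the Medicare projection, the Power section says: "We will then take our estimates of reduction in utilisation and apply these estimates to the current use of pre-op testing utilisation".

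**The concern.** Read literally, a cut of 59% from 90% ends at 36.9%, not 31%. The printed figure is a difference in percentage points written as a percentage. The next sentence halves it and again gives only a percentage, so a reader could take 30% as 30 points (65% to 35%) or as a 30% relative fall (65% to 45.5%). These differ by 10.5 points in the post-intervention rate and correspond to odds ratios of 0.29 and 0.45. For a before-after contrast they can fall on opposite sides of 80% power.

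There are two further worries. A 30-point fall from 65% is 46% relative, which is 70% of the prior relative effect, so calling it conservative and half as large seems open to dispute. And if percent and points are mixed here, the same could happen when a reduction is carried over to Medicare, where the baseline testing rate may not be 65%.

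**Working it through.** **1. Reproduce the plan's figures (rates from the Power section).**

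- Absolute: 90 − 31 = 59 points; 59/2 = 29.5, which rounds to the stated 30.
- Relative: 59/90 = 65.6%; half is 32.8%, which does not round to 30.

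Both printed numbers follow on the absolute scale and neither follows on the relative scale. The planning effect is 65 − 30 = 35, that is 65% to 35%.

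**2. The rival readings.**

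- 0.65 × (1 − 0.30) = 45.5%. This halves a points difference and then applies it as a relative reduction, so it mixes scales.
- 0.65 × (1 − 0.328) = 43.7%. This is what a consistent relative halving would give.

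**3. Is it half as large?** The answer depends on the scale.

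- Points: 30/59 = 51%.
- Relative: (30/65)/(59/90) = 0.462/0.656 = 70%.
- Log odds, the scale on which effects are to be reported: prior effect ln[(0.31/0.69)/(0.90/0.10)] = −2.997; planned effect ln[(0.35/0.65)/(0.65/0.35)] = −1.238; ratio 0.41.

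The claim holds on the absolute scale and more than holds on the log-odds scale. It fails only on the relative scale, which the plan did not use.

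**4. Power under each reading.** The documents give no power to reproduce, so these figures are conditional.

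Inputs: 1122 visits by 322 physicians in 2019 (Inclusion Criteria). Four equal arms are assumed, giving 1122/4 = 280.5 visits per arm and m = 1122/322 = 3.48 visits per physician. Two-sided α = 0.05/3 = 0.0167, with critical value 2.394. The ICC is assumed to lie between 0 and 0.10, physician volumes are taken as equal, and the two periods are treated as independent.

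Effective visits: n = 280.5/[1 + (3.48 − 1) × ICC], which is 280.5 at ICC 0 and 224.7 at ICC 0.10.

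Before-after contrast on the risk scale, with three cells at 65% and one at p:

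power = Φ{(0.65 − p)/√([3 × 0.65 × 0.35 + p(1 − p)]/n) − 2.394}

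Example for p = 0.35 at ICC 0: the standard error is √(0.91/280.5) = 0.0570; 0.30/0.0570 − 2.394 = 2.87; power 99.8%.

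| Reading | ICC 0 | ICC 0.10 |
|---|---|---|
| 65% to 35% | 99.8% | 99.0% |
| 65% to 43.7% | 90.5% | 82.1% |
| 65% to 45.5% | 83.9% | 73.8% |

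At α = 0.05/6 = 0.0083, which applies only if all six pairwise contrasts are corrected together, the ranges from ICC 0.10 to ICC 0 are 98.1% to 99.6%, 75.0% to 85.7% and 65.2% to 77.3%. A comparison of the post period alone at 0.0167 gives above 99.9% for 65% to 35% and 96.4% to 98.9% for 65% to 45.5%.

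A physician effect shared across the two periods would raise the before-after figures. Unequal physician volumes would lower them.

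**5. Does the label reach the savings?** The Power section multiplies estimated utilisation quantities by payment rates, and the Medicare step applies the reduction estimated in the trial. Neither step uses the planning 30%, and neither requires an odds ratio as input.

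**The case for a change.** The strongest opposing case has three parts.

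First, the words are wrong as printed, and this sentence supplies the only effect size in the design. That is true, but the bracketed rates in the same sentence correct it, and the reader who checks arrives at one answer.

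Second, the relative reading always has less power. For the before-after contrast at 0.0167 it can fall below 80%; in a post-period comparison it does so only under heavier clustering (at ICC 0.5, 76% against 99% for the absolute reading). This also stands, but as a conditional statement. It depends on an ICC, a contrast and an alpha split that the plan does not fix, and on the mixed-scale reading that the plan's own arithmetic does not support. What it really exposes is that no power calculation is given. That is a separate matter, and a clearer label would not supply one.

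Third, the Medicare projection does not name its scale. This is a fair remark. If the Medicare testing rate were 50% (an assumption for illustration), a 30-point fall would remove 30 tests per 100 patients, while the same effect applied as 46.2% relative would remove 23.1. However, the choice concerns how the observed result is transported, and it would be open even if the planning effect were perfectly labelled. The plan already estimates changes in utilisation rates between arms, so an analyst has either form to hand and would have to state which one was used.

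**Conclusion.** The concern is right that 59% should read as 59 percentage points (65.6% relative) and that the expected post-intervention rate is not printed. It does not show that the planning effect is misstated or undetermined. The plan's own numbers reproduce only on the absolute scale and give 65% to 35%, a 46% relative fall and an odds ratio of 0.29. On the log-odds scale this is 41% of the prior effect, so describing it as half as large is not contradicted there.

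On that reading, power per nudge-versus-control contrast is about 99% or more at 0.05/3, given 280.5 visits per arm, equal arms and physician volumes, independent periods and an ICC of at most 0.10. Power in the 70s arises for the before-after contrast only on readings that the arithmetic does not favour. Since the plan quotes no power, there is no stated figure to withdraw.

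Relabelling would alter no model, contrast, alpha level, sample size or reported estimate. The slip is clerical, and the unnamed scale of the Medicare projection is a detail that analysts can settle sensibly when they report it. No change to the plan follows.
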